18.2.4. ADDITIONAL EFFECTIVENESS ANALYSES

1. Compare mean monocular uncorrected distance (UCDVA), intermediate (UCIVA) and near (UCNVA) visual acuity of the IC-8 eyes to the fellow control eyes.

- 2. Binocular +0.75 D Distance Corrected Visual Acuity compared between the test group and the control group: +0.75 D distance correction will be achieved by correcting all eyes in both groups with their best distance-corrected refraction and then placing a +0.75 D lens in front of the IC-8 IOL eyes in the test group and in front of the second eyes in the monofocal control group.
 - Binocular +0.75 D Distance Corrected Intermediate Visual Acuity (+0.75 DCIVA): Proportion of subjects achieving 20/25 or better in the test group is at least 25% more than the control group.
 - Binocular +0.75 D Distance Corrected Near Visual Acuity (+0.75 DCNVA): Proportion of subjects achieving 20/40 or better in the test group is at least 25% more than the control group.
 - c. Binocular +0.75 D Distance Corrected Distance Visual Acuity (+0.75 DCDVA): Proportion of subjects achieving 20/25 or better in the test group is not less than the control group by more than 10%.
 - d. The monocular visual acuities from the IC-8 IOL eyes in the test group will be similarly compared to the second eyes in the control group.
- 3. Supportive analyses:
 - a. The monocular co-primary endpoint analyses on DCIVA and depth of focus will be repeated by comparing IC-8 IOL eyes to the second eyes in the control group to support the primary endpoint analyses.
 - b. The co-primary endpoint analyses on binocular UCDVA, UCIVA, UCNVA and monocular DCIVA will be repeated at 12 months to support the primary endpoint analyses performed at 6 months.
 - c. The secondary endpoint on tolerance to astigmatism in IC-8 IOL eyes is repeated on the postoperative refractive cylinder with the same grouping and test to support the results from preoperative corneal astigmatism and to check the influence from postoperative refractive cylinder on the effectiveness of the device.

18.3. SAFETY ANALYSES

All co-primary safety endpoints need to be achieved to claim overall safety success. Therefore no multiplicity adjustment is necessary for primary safety endpoints. For all key safety endpoints, the primary analysis population will be the safety analysis population.

18.3.1. CO-PRIMARY SAFETY ENDPOINTS

- 1. Monocular BCDVA in the IC-8 IOL eyes (at 12 months):
 - a. The mean BCDVA from the IC-8 IOL eyes is non-inferior to that from the fellow control eyes using a margin of 0.1 logMAR. The comparison between IC-8 IOL eyes and fellow eyes for mean monocular BCDVA (logMAR) will be performed using a t-test for non-inferiority at $\alpha = 0.05$ (one-sided). The null hypothesis is that the mean acuity for the IC-8 IOL eyes is inferior to the fellow eyes by 0.1 logMAR or more.

The alternative hypothesis is that the mean acuity for the IC-8 IOL eyes is inferior to the fellow eyes by less than 0.1 logMAR. Formally put as follows:

$$\begin{split} H_0: \mu_T - \mu_C \geq 0.1 \\ H_A: \mu_T - \mu_C < 0.1 \end{split}$$

Where μ_T is the mean logMAR acuity from the IC-8 eyes and μ_C is the mean acuity from the fellow eyes.

The statistical success criterion is when H_0 is rejected by a p-value less than 0.05, demonstrating the mean BCDVA from the IC-8 eyes is statistically non-inferior to the mean BCDVA from the control eyes using a margin of 0.1 logMAR.

b. The proportion of IC-8 eyes achieving BCDVA 0.3 logMAR or better is not less than the safety and performance endpoints (SPE) rate listed in ISO 11979-7:2014 Table B.3. The comparison between the proportion for the IC-8 eyes and the SPE rate for posterior chamber IOL (92.5%) will be performed using the exact test based on binomial distribution at $\alpha = 0.05$ (one-sided). The null hypothesis is that the proportion for the IC-8 eyes is not less than 92.5%. The alternative hypothesis is that the proportion for the IC-8 eyes is less than 92.5%. Formally put as follows:

> $H_0: p_T \ge 92.5\%$ $H_A: p_T < 92.5\%$

Where p_T is the proportion of IC-8 eyes achieving BCDVA 0.3 logMAR or better and 92.5% is the SPE rate for posterior chamber IOL.

The statistical success criterion is when H_0 is not rejected, i.e. the test result is a p-value greater than 0.05, demonstrating the proportion of IC-8 eyes achieving BCDVA 0.3 logMAR or better is not less than the SPE rate.

c. The proportion of best-case IC-8 eyes achieving BCDVA 0.3 logMAR or better is not less than the safety and performance endpoints (SPE) rate listed in ISO 11979-7:2014 Table B.4. The comparison between the proportion for the best-case IC-8 eyes and the SPE rate for posterior chamber IOL (96.7%) will be performed using the exact test based on binomial distribution at $\alpha = 0.05$ (one-sided). The null hypothesis is that the proportion for the best-case IC-8 eyes is not less than 96.7%. The alternative hypothesis is that the proportion for the best-case IC-8 eyes is less than 96.7%. Formally put as follows:

$$\begin{split} &H_0 {:} \ p_T \geq 96.7\% \\ &H_A {:} \ p_T < 96.7\% \end{split}$$

Where p_T is the proportion of best-case IC-8 eyes achieving BCDVA 0.3 logMAR or better and 96.7% is the SPE rate for posterior chamber IOL.

As specified in ISO 11979-7:2014, the statistical success criterion is when H_0 is not rejected, i.e. the test result is a p-value greater than 0.05, demonstrating the proportion of best-case IC-8 eyes achieving BCDVA 0.3 logMAR or better is not less than the SPE rate.

Note that a best-case subject is defined in Section 18.1 Analysis Population of this study protocol. For this analysis, only the IC-8 eye but not both eyes of a subject has to meet the best-case criteria.

- 2. Rates of ocular adverse events (the rate of adverse events are based on the proportion of eyes with events cumulative or persistent through database lock, as applicable):
 - a. For each type of adverse event listed in the ISO 11979-7:2014 Table B.2, the rate for the IC-8 IOL eyes is not statistically greater than the SPE rate for that event. The comparison between the adverse event rate for the IC-8 eyes and the SPE rate for posterior chamber IOL for each adverse event will be performed using the exact test based on binomial distribution at $\alpha = 0.05$ (one-sided). The null hypothesis is that the adverse event rate for the IC-8 eyes is not greater than SPE rate. The alternative hypothesis is that the adverse event rate for the IC-8 eyes is greater than the SPE rate. Formally put as follows:

$$\begin{split} H_0: p_T &\leq \hat{p} \\ H_A: p_T > \hat{p} \end{split}$$

Where p_T is the adverse event rate for the IC-8 eyes and \hat{p} is the SPE rate, for each adverse event listed in ISO 11979-7:2014 Table B.2.

As specified in ISO 11979-7:2014, the statistical success criterion is when H_0 is not rejected, i.e. the test result is a p-value greater than 0.05, demonstrating the adverse event rate for the IC-8 eyes is not greater than SPE rate. The statistical success criterion is equivalent to showing the one-sided 95% lower confidence limit of the rate is not greater than the historical control rate based on an exact binomial distribution.

- b. Descriptive statistics (mean, two-sided 90% confidence interval) for the rates of all key adverse events including but not limited to adverse events per ISO 11979-7:2014, adverse events that may be specifically related to the EDOF IOL design, e.g., related to the optical characteristics of the lens, and any other significant ocular adverse events. Summary statistics will be provided for the IC-8 eyes and fellow eyes in the test group, and for first eyes and second eyes in the control group.
- 3. Rate of IC-8 IOL removals due to visual/optical reasons (the rate is based on eyes with events, cumulative through 12 months):

Rate of removals due to visual/optical reasons in the IC-8 IOL eyes is < 3.1%. The one-sided 95% upper confidence limit of the rate (using exact binomial distribution) must be less than 3.1% to claim statistical success.

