6.0 STUDY DESIGN

This will be a prospective, multi-center, open-label, parallel group, non-randomized, examinermasked, one-year study of a small-aperture IOL that provides extended depth of focus to patients after the surgical removal of the crystalline lens. The patients will be consented for three years; the first year (with data from all fully enrolled and qualified subjects with successful or attempted IC-8 IOL implantation through 12-month follow-up) will support the Premarket Approval (PMA) with a possibility of two years of post-approval follow-up. The test group will consist of subjects who are implanted with the investigational IC-8 IOL in one eye and implanted with a monofocal or monofocal toric IOL in the fellow eye. The control group will consist of subjects who are bilaterally implanted with monofocal or monofocal toric IOLs. The monofocal control IOL will be a marketed colorless, aspheric (-0.20 to -0.28 micrometers) IOL.

The binocular performance of the subjects in the test group will be compared to the binocular performance of the subjects in the control group. The monocular performance of the eyes implanted with the IC-8 IOL will be compared to the monocular performance of the fellow control eyes implanted with the monofocal IOL in subjects from the test group.

The study enrollment period is estimated to be six to nine months; start of enrollment at each site is dependent on IRB approval. Subjects will be followed for approximately 12 months postoperatively. Study duration for all activities, including start of enrollment to completion of all postoperative visits, is estimated to be approximately 18 to 24 months.

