18.0 DATA ANALYSIS METHODS

This section (section 18.0 through 18.4) highlights the key statistical methods and analyses planned for this study. The SAP includes details for all statistical methods, plans, adverse events reporting methods, and sample size calculations for the study.

Some key data and analysis conventions include the following:

For the primary and secondary effectiveness endpoints, the six-month postoperative visit will be the primary analysis time point unless otherwise noted. For the primary safety endpoints, the 12-month study visit will be the primary analysis time point.

Binocular safety and effectiveness analyses will compare the test group and the control group. Monocular safety and effectiveness analyses will compare the IC-8 IOL eyes and the monofocal fellow eyes within the test group. All co-primary effectiveness and safety endpoints have to be met to claim overall effectiveness and safety success. There is one secondary effectiveness endpoint regarding the tolerance to astigmatism in IC-8 IOL eyes, and this endpoint will only be tested when all co-primary effectiveness endpoints have been achieved. Under this plan, type I error rates will be controlled at a significance level of 0.05 per individual hypothesis without adjustment for multiplicity under any family. Other statistical comparisons in the additional analyses and supportive analyses should not be used for the purpose of claims.

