For all key safety endpoints, the primary analysis population will be the safety analysis population. The safety population will consist of all subjects who complete enrollment and have been bilaterally implanted and those subjects not successfully implanted with the IC-8 IOL but for whom the IC-8 IOL touched the eye. Safety analyses will only include available data at the time of analysis (i.e., no data imputation). Reporting of cumulative complications (occurring at any time postoperative) will include data from all subjects in the safety population. Test subjects who have undergone the IC-8 IOL surgery with attempted but failed implantation will be followed until all ocular adverse events are resolved or stable before being exited from the study, and they will be counted in the safety population.

The safety population (with no imputation) will also be used for reporting of other postoperatively measured clinical parameters that are not discussed as part of the key effectiveness or safety endpoints.

The primary reporting will be on IC-8 IOL eyes and fellow eyes in the test group or binocular outcomes from both test and control groups. However, key data such as visual acuity, refractive error, medical/lens complications and adverse events will also be reported separately for first and second eyes in the control group.

Besides the ITT (or mITT) and PP populations, key effectiveness outcomes and key safety outcome of BCDVA may also be reported for best-case subjects where appropriate. A best-case subject is defined in ISO 11979-1:2012 as a subject with no preoperative ocular pathology, no macular degeneration detected at any time, and no previous surgery for the correction of refractive errors. In this study, a best-case subject should also have no significant macular pathology at any time. Both eyes must meet the best-case criteria for inclusion in the best-case analysis.

Subjects who are disqualified prior to second-eye implantation will not be counted toward the study cohort or any analysis population. For the disqualified subjects, a listing of UCDVA and BCDVA at preoperative and before study exit will be tabulated, as well as any adverse events; no other analysis will be performed.

In addition to the above analysis populations, additional best-case analyses and exploratory subgroup analyses may also be performed as specified in the SAP.

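### The adverse-event rates tested against the SPE rates run to database lock, in conflict with the protocol's own 12-month time point for primary safety; the effect is probably small and the wording is easily aligned

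*Combined protocol and SAP*

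**What the plan says.** Section 18.0 gives one rule: "For the primary safety endpoints, the 12-month study visit will be the primary analysis time point". The allowance for exceptions in that paragraph is attached to the effectiveness endpoints, not to safety.

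Section 18.3.1 has three co-primary safety endpoints, all of which must be met (section 18.3):

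- Item 1, best-corrected distance acuity, is assessed at 12 months.
- Item 2, ocular adverse events, uses a different window: "the rate of adverse events are based on the proportion of eyes with events cumulative or persistent through database lock, as applicable". Each event type in ISO 11979-7:2014 Table B.2 has an exact binomial test at one-sided 0.05. Success is equivalent to showing that "the one-sided 95% lower confidence limit of the rate is not greater than the historical control rate".
- Item 3, removals for visual or optical reasons, is again fixed: "the rate is based on eyes with events, cumulative through 12 months".

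Section 18.1 sets no upper time limit: "Reporting of cumulative complications (occurring at any time postoperative) will include data from all subjects in the safety population". It also rules out imputation for safety. On timing, section 6.0 states: "The study enrollment period is estimated to be six to nine months", and "Subjects will be followed for approximately 12 months postoperatively".

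**The concern.** Item 2 is a pass/fail test of a proportion against a fixed reference, so the proportion needs a defined period at risk. Database lock is a calendar date, and the text gives none. With staggered entry, a calendar cut-off gives early subjects a longer potential window than late ones. The tested rate then depends partly on enrolment speed and lock date as well as on the device.

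The word *persistent* is not defined, and the text does not say which events are counted cumulatively and which as persistent. An event present at month 12 and resolved before lock could be counted or left out, and that choice can fall in either direction.

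At stake is whether item 2 can be read on the same footing as items 1 and 3, and whether its result could turn on an administrative date.

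**Working it through.** **Inputs from the protocol.** Enrolment 6 to 9 months and follow-up about 12 months (section 6.0). The 12-month visit falls at days 300–420 after second-eye surgery, and the two surgeries are at most 45 days apart (section 9.2, Table 4). Target of 300 completing test subjects; 355 enrolled with 5% disqualification (section 7.0). Exact binomial test, one-sided 0.05 (section 18.3.1).

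**Assumptions, because the documents do not give the figures.** SPE rates of 1% and 2%; uniform entry; lock when the last subject reaches month 12; constant hazard; every subject observed to lock; true 12-month rate equal to the SPE rate.

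**1. The plan's own figure.** Section 6.0 gives a total duration of about 18 to 24 months. Lower end: 6 + 12 = 18. Upper end: 9 + (45 + 420)/30.44 = 24.3. The stated range is reproduced, and it leaves no room for scheduled observation of all subjects beyond their 12-month visits.

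**2. Potential time at risk to lock.** With enrolment of E months, the first subject has 12 + E months and the last has 12.

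| E | First subject | Ratio to last | Mean, 12 + E/2 |
|---|---|---|---|
| 6 | 18 months | 18/12 = 1.50 | 15 months |
| 9 | 21 months | 21/12 = 1.75 | 16.5 months |

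For comparison, a cut at the 12-month visit itself still spans 420/300 = 1.4-fold.

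**3. Pass limits at n = 300.** The test fails at the smallest count r with P(X ≥ r | 300, SPE) ≤ 0.05. At SPE 1%, r = 7 (pass at 6 or fewer), with failure probability 3.3%. At SPE 2%, r = 11 (pass at 10 or fewer), with failure probability 4.1%.

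**4. Rate at lock.** q = 1 − (1 − p)^(m/12), with m the mean exposure applied to all subjects.

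| SPE | Cut at 12 months | m = 15 | m = 16.5 |
|---|---|---|---|
| 1% | 3.3% | q = 1.25%, fails 8.5% | q = 1.37%, fails 12.2% |
| 2% | 4.1% | q = 2.49%, fails 13.3% | q = 2.74%, fails 20.4% |

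**5. Sensitivity to the assumptions.**

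- If half of the extra exposure is captured (m = 13.5 or 14.25), failure is 5.5–6.9% at SPE 1% and 7.9–10.4% at SPE 2%. If a quarter is captured, it is 4.3–4.9% and 5.8–6.8%.
- If only 20% of 12-month events arise after month 3 (an assumption), at a steady rate that continues to lock with full observation, the rate at lock is p × [1 + 0.2 × (m − 12)/9]. Failure is 4.4–5.0% at SPE 1% and 5.9–7.0% at SPE 2%.
- The safety population could be nearer 355 × 0.95 ≈ 337. Under the assumptions of step 4, failure then moves from 2.1% to 6.3–9.6% at SPE 1%, and from 4.1% to 14.1–21.8% at SPE 2%.

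**The case against.** The strongest reply is that the plan does not describe observation to lock. Section 6.0 has subjects followed for about 12 months and ties the premarket submission to data through that point. Table 4 and Appendix A schedule nothing later. What reaches the database after a subject's 12-month visit would be mainly unscheduled visits, late reports and follow-up of known events. Several listed events also belong to the early period: section 10.2.1 places toxic anterior segment syndrome within 24 to 48 hours of surgery. All of this stands, and it is why the figures in step 4 are upper-end illustrations and not expectations.

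A second reply is that counting every event known at lock is conservative. That also stands for cumulative events: later events can only raise the rate and make the test harder to pass. A reader might infer that the wording gives the device an easier route to success. For cumulative events the documents show the opposite. Only for persistent events can the direction reverse, and no size can be put on that.

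A reader might also infer from the three-year consent that lock could come years later. The documents describe the extra two years as post-approval, so this adds little.

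Finally, sections 18.0 and 18.4 refer adverse-event reporting detail to the SAP. A cut-off set there would settle the analysis, but item 2 would still need to be brought into line with section 18.0.

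**Conclusion.** The conflict is in the current text. One of three co-primary safety endpoints has a calendar-based window, while the general rule and the other two endpoints use 12 months, and *persistent* is undefined. Under the stated rule, potential time at risk differs by up to 1.5- to 1.75-fold between first and last subject, if lock falls at the last 12-month visit.

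The practical effect on cumulative rates is probably small and runs against the device. The failure probabilities of about 8–12% (SPE 1%) and 13–20% (SPE 2%), against 3–4% with a 12-month cut, rest on assumed SPE rates, constant hazard and full observation to lock.

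Two stronger readings are not supported. The documents do not show that early enrollees will actually be observed six to nine months longer. Nor do they allow the claim that the window departs from the period behind the ISO rates, because neither Table B.2 nor its reference period is given.

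**What to change.** In section 18.3.1 item 2, for the SPE tests:

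- Count cumulative events through each subject's 12-month visit. For a subject without that visit, count through the end of the 12-month window (day 420) or study exit.
- Define a persistent event as one present at the 12-month visit, or at the last available visit if that one is missing, and say which event types use which rule.
- Report the rates through database lock alongside as a supportive analysis, and list the events that arise after the 12-month cut-off.

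The cost is a short wording change, a supportive table and a listing, all from data already collected. The downside is that events known after 12 months leave the primary test, which is why the lock-based rates should still be shown. The change does not remove the 300–420 day spread of the visit itself, nor the shorter exposure of subjects who leave early (about 10% attrition is planned for, with no imputation).

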7.0 STUDY POPULATION

Potential study subjects will be recruited from patients with bilateral cataracts who plan to undergo crystalline lens removal by phacoemulsification followed by intraocular lens implantation in the capsular bag. Eligibility for the study will be determined at the preoperative visit. If the patient meets all inclusion/exclusion criteria, he or she must give informed consent to be provisionally enrolled in the study as a subject.

To allow for approximately 10% attrition rate over the duration of the one-year study and another 5% disqualification rate for the first implanted eye, a total of 355 test subjects and 120 control subjects will be consented and provisionally enrolled to ensure 300 test and 100 control subjects are available to complete the one-year follow-up to support the PMA.

Each study site (assuming a total of 23 sites) should enroll approximately 15 subjects in the test group and 5 subjects in the control group, but no more than 25% of the total population of the study. The number of subjects intended to be enrolled in the study for each treatment arm (before

the first implanted eye's qualification to complete enrollment) is shown in **Table 3**. Furthermore, based on previous data from the IC-8 IOL European clinical study, the distribution of preexisting corneal astigmatism between 0 and 1.5 D in the intended population consists of roughly 83-85% of patients between 0 to less than 1.0 D and roughly 15-17% of patients between 1.0 to 1.5 D. The anticipated enrollment ratio is thus approximately 5:1 for < 1.0 D of preoperative corneal astigmatism (Astigmatism Group 1) vs. 1.0 to 1.5 D of preoperative corneal astigmatism (Astigmatism Group 1) vs. 1.0 to 1.5 D of preoperative corneal astigmatism group as shown in **Table 3** should reflect the anticipated enrollment by group in the study. The overall enrollment from all sites will be monitored closely to ensure that the enrollment target should be met for each treatment arm and astigmatism group. When each and all targets are met, the sponsor will inform all sites to cease enrollment. More details on controlling the enrollment process for potential imbalance in baseline characteristics is specified in the Statistical Analysis Plan (SAP).

	Astigmatism Group 1** (< 1.0 D of preoperative corneal astigmatism)	Astigmatism Group 2** (1.0 D to 1.5 D of preoperative corneal astigmatism)

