7.3. QUALIFICATION CRITERIA TO COMPLETE ENROLLMENT

The 1st eye implanted with a monofocal or monofocal toric IOL must achieve the following criteria in order for the subject to qualify and proceed to implantation in the 2nd eye:

- 1. 20/32 or better uncorrected distance visual acuity (UCDVA) and 20/25 or better bestcorrected distance visual acuity (BCDVA) (or Snellen equivalent)
- 2. No ongoing ocular adverse events
- 3. Normal corneal health as assessed by slit lamp biomicroscopy:
 - a. Corneal edema (refer to Appendix C in the protocol): Grade 1+ or less
 - b. Superficial punctate keratitis (SPK, refer to Oxford grading scale): Grade 1 or less

The subject must qualify within the 1-week to 1-month visit windows (7 to 45 days from the 1st eye surgery). Subjects in both the test and control groups whose first implanted eye does not achieve the qualification criteria will be disqualified and exited from the study and will not be counted toward the study cohort or analysis population.

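### The descriptive adverse-event rates for test fellow eyes and control first eyes (18.3.1, item 2b) omit subjects who failed first-eye qualification, so they are likely to be too low beside the IC-8 rates

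*Combined protocol and SAP*

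**What the plan says.** Section 7.3 (repeated in 9.1 and 9.4) requires the monofocal first eye to pass a check between days 7 and 45 before the second eye is operated. The criteria are distance-acuity limits, corneal limits and "No ongoing ocular adverse events". A subject who fails leaves the study.

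Section 18.1 states: "Subjects who are disqualified prior to second-eye implantation will not be counted toward the study cohort or any analysis population". For these subjects, distance acuities before surgery and before exit "will be tabulated, as well as any adverse events; no other analysis will be performed". The safety population, which supplies the cumulative complication rates, is "all subjects who complete enrollment and have been bilaterally implanted" together with "those subjects not successfully implanted with the IC-8 IOL but for whom the IC-8 IOL touched the eye".

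Section 9.6.4 discontinues a subject who has a surgical complication, such as capsular or zonular damage, in either eye of either arm.

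Section 18.3.1, item 2 has two parts. Part (a) tests each event rate in IC-8 eyes against the ISO safety and performance endpoint (SPE) rate. Part (b) is descriptive: "Summary statistics will be provided for the IC-8 eyes and fellow eyes in the test group", and for first and second eyes in the control group, with two-sided 90% intervals. As a general convention, Section 18.0 says: "Monocular safety and effectiveness analyses will compare the IC-8 IOL eyes and the monofocal fellow eyes within the test group".

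Section 7.0 sizes enrolment for about 10% attrition and "another 5% disqualification rate for the first implanted eye".

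**The concern.** One reason for leaving the study at qualification is the very thing item 2b counts. A first eye with an ocular adverse event still active at the check is taken out of both numerator and denominator, and its event appears only in a listing. IC-8 eyes and control second eyes are operated after the check and are not screened in this way. The safety population also restores failed IC-8 implantations where the lens made contact, with no matching rule for monofocal first eyes.

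The plan makes IC-8 eyes and fellow eyes its primary monocular reporting. A reader will set the two columns side by side, especially for events that have no SPE rate. If the true risks were equal, the IC-8 column could still look worse because the fellow-eye column has been filtered.

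**Working it through.** **1. Reproduce the enrolment figures.** Inputs (Section 7.0): 300 and 100 completers, 10% attrition, 5% first-eye disqualification.
- Sequential losses: 300 / (0.90 × 0.95) gives 351, and 100 / (0.90 × 0.95) gives 117.
- Additive losses: 300 / 0.85 gives 353, and 100 / 0.85 gives 118.
- The plan has 355 and 120. Forward check: 355 × 0.90 × 0.95 = 303.5, and 120 × 0.90 × 0.95 = 102.6.

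The plan's figures are consistent with its allowances.

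**2. First eyes outside every rate.**
- Test: 0.05 × 355 = 17.75, about D = 18, leaving q = 337.
- Control: 0.05 × 120 = 6, leaving q = 114.

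The 5% covers acuity, corneal and adverse-event failures together, and the documents do not split it.

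**3. Effect on a rate.** Let x be the eyes with the event among the q qualified, and k the eyes with it among the D disqualified.

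Reported rate = x / q. Rate over all operated first eyes = (x + k) / (q + D).

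The difference equals D/(q + D) × (k/D − x/q). The reported rate is too low only if the event is commoner among disqualified than among qualified eyes. That is likely, since an ongoing event is itself a ground for disqualification.

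Both x and k are assumptions. Intervals are exact 90% (Clopper-Pearson).

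| Reported rate | 90% interval | Rate over all operated first eyes, by k |
|---|---|---|
| Test 7/337 = 2.1% | 1.0 to 3.9% | k=0: 2.0%; k=2: 2.5%; k=4: 3.1%; k=9: 4.5%; k=18: 7.0% |
| Test 17/337 = 5.0% | 3.2 to 7.5% | k=0: 4.8%; k=2: 5.4%; k=4: 5.9%; k=9: 7.3%; k=18: 9.9% |
| Control 2/114 = 1.8% | 0.3 to 5.4% | k=0: 1.7%; k=1: 2.5%; k=2: 3.3%; k=3: 4.2%; k=6: 6.7% |

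In the test arm with a reported rate of 2.1%, the shift is +0.5 points at k = 2, +1.0 at k = 4 and +2.4 at k = 9. If every disqualified first eye had the event, it would be about +5 points. Shifts up to k = 4 stay inside the reported interval in both test rows. At k = 9 the corrected rate leaves the interval in the 2.1% row (4.5% against 3.9%) but not in the 5.0% row (7.3% against 7.5%).

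**4. What does not move.** No disqualified subject received an IC-8 lens, so the IC-8 rates, and hence the tests in item 2a, are unchanged.

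**5. Surgical complications.** A subject discontinued under 9.6.4 at the first eye is apparently never bilaterally implanted within the study, so falls outside the safety population. The plan calls this subject discontinued, whereas the Section 18.1 listing is for disqualified subjects. It is unclear whether the listing covers these events. They are not in the figures above.

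**The case against.** The strongest reply is that nothing inferential depends on these rates. Item 2b has no hypothesis, no difference and no success criterion. The only adverse-event tests use IC-8 eyes against SPE rates. A reader might infer from the Section 18.0 convention that a formal between-eye safety comparison is biased. The documents do not support that for adverse events: the safety comparisons they spell out against fellow eyes are best-corrected acuity and contrast sensitivity. The error also makes the device look worse, so it cannot produce a false safety success. All of this stands.

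Other parts also stand:
- The disqualifying events are not lost. Section 18.1 lists them, and first-eye events that resolved before the check are counted for subjects who qualified.
- Several listed events can hardly be established by day 45. Section 10.2.1 defines corneal edema and cystoid macular edema by acuity at 1 month or later, and chronic anterior uveitis by a course judged over 3 months.
- Second eyes are not free of all removal. Under 9.6.4 and 18.1, a complication before the IC-8 lens touches the eye may drop that subject too, unless a back-up lens counts as bilateral implantation. Control second eyes have no add-back.
- The screen partly mirrors the indication, which requires good fellow-eye acuity first. Rates conditional on it describe the intended users.

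A reader might also infer that control second eyes should replace fellow eyes as the comparator. That is a trade-off. The contrast is non-randomised, and at 5% risk the 90% half-width of the difference is 1.645 × √(0.05 × 0.95 × (1/337 + 1/114)) = 3.9 points, larger than most of the shifts shown above. Control second-eye rates are already in item 2b.

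The reply does not remove the asymmetry. The planned table shows screened first eyes beside unscreened IC-8 eyes, and Section 18.1 rules out any rate that would show the difference.

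**Conclusion.** The point holds as a reporting defect in a descriptive table. The test fellow-eye and control first-eye rates in item 2b are conditional on having no ongoing ocular adverse event at qualification, and are likely to be too low beside the IC-8 rates. The understatement lies between none and a few percentage points. The ceiling of about 5 points requires every disqualified first eye to have had the event. These sizes rest on the plan's 5% allowance and on assumed event counts, because the documents give neither the adverse-event share of disqualifications nor any event rates.

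The co-primary safety conclusion is not affected. Sections 18.0 and 18.4 leave adverse-event reporting detail to SAP text that was not in the material reviewed. That text should be checked first, although a rate there that included these subjects would conflict with Section 18.1 as written.

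**What to change.** Keep the planned item 2b tables and the fellow-eye comparator, and make three changes.

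1. In 18.3.1, item 2b, add descriptive adverse-event rates with two-sided 90% intervals over all operated first eyes, by arm. Include disqualified subjects and those discontinued for a first-eye surgical complication.
2. In 18.1, amend the rule that allows only a listing for disqualified subjects so that this one analysis is permitted. State that the listing also covers first-eye surgical-complication discontinuations.
3. Footnote item 2b: fellow-eye and control first-eye rates are conditional on qualification, and control second-eye rates come from subjects who passed the same first-eye screen.

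The cost is wording and programming. Disqualified subjects' events are already to be tabulated, and Section 10.4 has subjects withdrawn for an adverse event followed until it is resolved or stable. The downside is unequal follow-up: disqualified subjects exit early, so their later first-eye events stay unknown. The added table should say so.
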